**4.3.1.3 SAEs****4.3.1.3.1 Presence**

An observation will be considered an event if it has at least a verbatim term.

**4.3.1.3.2 Last Vaccination**

For subjects aged 6 months to 8 years:

Last vaccination before an SAE is derived from the last visit numbers provided in the clinical database and is calculated as follows:

**450 – Quadrivalent Influenza Vaccine**

---

If an SAE has a non-missing visit number, the visit number should be used to determine the last vaccination before the SAE

If the visit number is missing, then the start date should be used to determine the last vaccination before the SAE

For subjects aged 9 years or older:

Last vaccination before any SAE is the study vaccination at V01.

**4.3.1.3.3 Time of Onset**

Time of onset will be computed using the same methodology than for unsolicited non-serious AEs described in Section 4.3.1.2.4.

SAEs will be analyzed throughout the study using the following periods:

- Within 28 days after each / any injection
- During the study (i.e., all SAEs occurred during the study)

An SAE with missing time of onset will be considered to have occurred just after the vaccination indicated by the visit number, so will be included in these tables.

Note: Any SAEs that occurred before vaccination (negative time of onset) will not be included in analysis but will be listed separately.

**4.3.1.3.4 Duration**

Duration will be computed using the same methodology as for unsolicited non-serious AEs described in Section 4.3.1.2.5.

**4.3.1.4 Other Safety Endpoints****4.3.1.4.1 Action Taken**

This information will be listed as collected, including missing observations. No derivation or imputation will be done.

**4.3.1.4.2 Seriousness**

This information will be summarized as collected. No derivation or imputation will be done.

**4.3.1.4.3 Outcome**

This information will be summarized as collected. No derivation or imputation will be done.

**4.3.1.4.4 Causality**

This information will be summarized as collected. Missing causality (relationship) will be handled as described in Section 5.3.2.2.

#### 4.3.1.4.5 AEs Leading to Study Discontinuation

A flag is available in the clinical database for all AEs in order to identify AEs leading to discontinuation.

In general, the items that are counted are:

- Disposition table: A subject who has, on the termination form, the reason for early termination “Serious Adverse Event” or “Other adverse event” is checked.
- Safety overview table: A subject who has either on the termination form, the reason for early termination “Serious Adverse Event” or “Other adverse event” is checked or lists an AE on an AE page (solicited, unsolicited, or SAE) that has “Reaction Leading to Termination” or “Event Leading to Termination” or “Serious Adverse Event Leading to Termination” checked that is at least Grade 1 and is within the time period indicated. Note: If the Grade is below 1, the AE will be excluded from the list of AEs leading to study discontinuation.
- System organ class/Preferred term (SOC/PT) table: An event (solicited, unsolicited, or SAE) that has “Reaction Leading to Termination” or “Event Leading to Termination” or “Serious Adverse Event Leading to Termination” checked that is at least Grade 1 and is within the time period indicated.

#### 4.3.1.4.6 AEs of Special Interest (AESIs)

AESIs will be collected throughout the trial (i.e., up to 28 days after the final vaccination). AESIs are to be reported as SAEs. These include new onset of Guillain-Barré syndrome (GBS), Bell’s palsy, encephalitis/myelitis, optic neuritis, Stevens-Johnson syndrome, toxic epidermal necrolysis, and febrile seizures.

#### 4.3.1.4.7 Pregnancy

This information will be listed as collected. No derivation or imputation will be done.

#### 4.3.1.4.8 Medical history

Medical history will be coded using MedDRA most updated version.

### 4.3.2 Immunogenicity

#### 4.3.2.1 Computed Values for Analysis

In order to appropriately manage replicate values for analysis purposes, the individual geometric mean (GM) of all values will be computed for each bleed (BL) after managing extreme values as described:

If a value is  $< \text{LLOQ}$ , then use the computed value  $\text{LLOQ}/2$ .

If a value is between  $\geq \text{LLOQ}$  and  $< \text{ULOQ}$ , then use the value.

If a value is  $\geq \text{ULOQ}$ , then use the computed value  $\text{ULOQ}$ .

#### 4.3.2.2 Seroprotection

If the computed value is  $\geq 1:40$  1/dil, then the derived seroprotection indicator will be “Yes” for that test, otherwise seroprotection will be “No”. If the computed value is missing, seroprotection will be missing.

#### 4.3.2.3 Fold-rise

The derived endpoint fold-rise is driven by both baseline and post-baseline computed values (assuming replicate values have been reduced to one value as described in Section 4.3.2.1) and is computed as follows. Generally, for extreme values, this algorithm minimizes the numerator and maximizes the denominator.

- If the baseline computed value is  $< \text{LLOQ}$  and the post-baseline computed value is  $< \text{LLOQ}$  then the fold-rise is 1.
- If the baseline computed value is  $\geq \text{LLOQ}$  and the post-baseline computed value is  $\geq \text{LLOQ}$  then the fold-rise is post-baseline computed value / baseline computed value.
- If the baseline computed value is  $\geq \text{LLOQ}$  and the post-baseline computed value is  $< \text{LLOQ}$  then the fold-rise is  $(\text{LLOQ}/2)$  / baseline computed value.

If the baseline computed value is  $< \text{LLOQ}$  and the post-baseline computed value is  $\geq \text{LLOQ}$  then the fold-rise is post-baseline computed value /  $\text{LLOQ}$ .

#### 4.3.2.4 Seroconversion

Seroconversion is defined as either

- a computed value  $< 10$  1/dil at D0 and post-injection computed value  $\geq 40$  1/dil at D28 or
- a computed value  $\geq 10$  1/dil at D0 and a  $\geq 4$ -fold increase in computed titer values 1/dil at D28 as described in Section 4.3.2.3.

#### 4.3.3 Efficacy

Not applicable.

#### 4.3.4 Derived Other Variables

##### 4.3.4.1 Age for Demographics

The age of a subject in the study is the calendar age as defined in the protocol.

##### 4.3.4.2 Duration of a Subject in the Trial

The duration of a subject in the trial is computed as follows:

Maximum (visit dates, termination date, last contact date) – V01 date +1.

#### 4.3.4.3 Duration of the Study

The durations are computed in days as follows: Latest period date - earliest period date + 1.

Maximum (visit dates, termination date, last contact date) – minimum (V01 dates) +1

## 5 Statistical Methods and Determination of Sample Size

The statistical analyses will be performed under the responsibility of the Sponsor's Biostatistics platform using SAS® Version 9.4 software or later.

The results of the statistical analysis will be available in the interim clinical study report (CSR) and in the final CSR.

For descriptive purposes, the following statistics will be presented:

**Table 5.1: Descriptive statistics produced**

Baseline characteristics and follow-up description	Categorical data	Number of subjects. Percentage of subjects.
	Continuous data	Mean, standard deviation, quartiles, minimum, and maximum.
Clinical safety results	Categorical data	Solicited: Number and percentage (95% CIs) of subjects. Unsolicited: Number and percentage (95% CIs) of subjects, and number of events.
Immunogenicity results	Categorical data (seroprotection, seroconversion, cutoff)	Number and percentage (95% CIs) of subjects.
	Continuous data (titer / data†)	Log10: Mean and standard deviation. Anti-Log10 (work on Log10 distribution, and anti-Log10 applied): Geometric mean, 95% CI of the geometric mean, quartiles, minimum, and maximum. Graphical representation by Reverse Cumulative Distribution Curve (RCDC).

The confidence interval (CI) for the single proportion will be calculated using the exact binomial method (Clopper-Pearson method, quoted by Newcombe (2)), i.e., using the inverse of the beta integral with SAS.

For immunogenicity results, assuming that Log10 transformation of the titers follows a normal distribution, at first, the mean and the 95% CI will be calculated on Log10 (titers) using the usual calculation for normal distribution (using Student's t distribution with n-1 degree of freedom), then antilog transformations will be applied to the results of calculations, in order to provide GMs and their 95% CI.

## 5.1 Statistical Methods

### 5.1.1 Hypotheses and Statistical Methods for Immunogenicity Objective

#### 5.1.1.1 Hypotheses

No statistical hypotheses will be tested.

#### 5.1.1.2 Statistical Methods

The following parameters will be presented:

GM of titers on pre-vaccination (D0) and post-vaccination (D28/D56a)

GM of titers ratio D28/D0 or D56/D0

Rate of subjects with titer  $\geq 10$  (1/dil) on D0 and D28 or D56

Seroprotection rate (titer  $\geq 40$  [1/dil]) on D0 and D28 or D56

Seroconversion or significant increase rate from D0 to D28 or D56

Immunogenicity analyses will be performed according to the following age sub-groups following the schedule applied:

- 6 to 35 months
- 3 to 8 years
- 9 to 17 years
- 18 years or older: additionally a subgroup analysis will be done on 18 to 64 years, and 65 years and older

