#### 4.1.1 Immunogenicity Endpoints

Immunogenicity will be evaluated before and 28 days after the final vaccinationa using the HAI technique. For each vaccine strain, serum HA antibody titers will be expressed as geometric mean (GM) of HAI titers obtained in duplicates for pre- (D0) and post-vaccination (28 days after the final vaccinationa).

The derived endpoints will be:

Individual geometric mean of duplicate titers (GM of titers) pre- and post-vaccination

Detectable HAI: titer  $\geq 10$  (1/dilution [1/dil]) pre- and post-vaccination

Individual titer ratio post-vaccination/pre-vaccination

Seroconversion status: titer  $\geq 40$  (1/dil) pre- and post-vaccination

Seroconversion or significant increase status:

- Seroconversion status: pre-vaccination titer  $< 10$  (1/dil) and post-vaccination titer  $\geq 40$  (1/dil)
- Significant increase status: pre-vaccination titer  $\geq 10$  (1/dil) and  $\geq 4$ -fold increase of post-vaccination titer

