***Anti-Influenza Virus Antibody Titration by Inhibition of Hemagglutination***

Assays will be performed by the Sponsor's laboratory (GCI, Swiftwater, PA, USA) or at a contract research organization laboratory under GCI responsibility. The address is provided in the Operating Guidelines.

Test serum samples and quality control sera are incubated with Neuraminidase to eliminate non-specific inhibitors. Adsorption of spontaneous anti-species agglutinins is then performed by incubating the serum samples and quality control sera with a red blood cell (RBC) suspension. The mixtures are then centrifuged and the supernatants containing the treated sera are collected for testing.

Ten two-fold dilutions of the initial 1/10 dilution of the treated serum samples and quality control sera are incubated with previously titrated HA antigen (4 hemagglutination units [HAU]/25 µL). HA antigen is not added to serum control wells containing only serum and RBCs. The mixture is then incubated and a RBC suspension is added. Following incubation, the results are read. The serum titer against each influenza strain tested is determined as the reciprocal of the highest dilution that exhibits complete inhibition of hemagglutination. Each serum sample is titrated in independent duplicates and the two values, which cannot differ by more than a two-fold dilution, are reported. The lower limit of quantitation (LLOQ) is set at the reciprocal of the lowest dilution used in the assay, i.e., 10 (1/dil). Titers below this level are reported as <10 (1/dil). The upper limit of quantitation (ULOQ) is 10240 (1/dil). Titers above this level are reported as ≥ 10240 (1/dil).

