## 5.4 Interim / Preliminary Analysis

Preliminary data line listings on subjects aged 18 years or older, 9 to 17 years, and 3 to 8 years will be prepared in the scope of the 3 early safety reviews.

No formal interim analyses are planned. However, the statistical analysis may be performed in 2 steps:

A first analysis of the immunogenicity and safety data from the 100 adult subjects will be performed once data are available and after first data base lock.

A final analysis at the end of the study when immunogenicity and safety data from all subjects are available and the final database lock.

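### Does the plan leave the reported post/pre titre ratio undefined for subjects who start below the limit of quantitation?

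*SAP*

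**What the plan says.** Section 4.1.1 lists among the derived endpoints the "Individual titer ratio post-vaccination/pre-vaccination", with no formula and no rule for low values. Section 5.1.1.2 carries it into the analysis as the "GM of titers ratio D28/D0 or D56/D0", with no cross-reference.

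The calculation rules stand in Section 4.3.2:

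- Section 4.3.2.1 handles replicates: "the individual geometric mean (GM) of all values will be computed for each bleed (BL) after managing extreme values as described". A value below the lower limit of quantitation (LLOQ) counts as LLOQ/2. The HAI assay text in Section 4.1.2 sets the LLOQ at 10, so this is 5.
- Section 4.3.2.3 takes those values as input: "The derived endpoint fold-rise is driven by both baseline and post-baseline computed values". It has four branches. When baseline is below LLOQ and the later value is not, it divides by LLOQ. It states its intent: "Generally, for extreme values, this algorithm minimizes the numerator and maximizes the denominator".
- Section 4.3.2.4, on seroconversion, is the only place that cites the fold-rise rule, for a "fold increase in computed titer values 1/dil at D28 as described in Section 4.3.2.3".

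**The concern.** The words titre ratio and fold-rise are never tied together. Fold-rise appears by that name in neither Section 4.1.1 nor Section 5.1.1.2. A programmer who reads the ratio literally, and applies the Section 4.3.2.1 values, divides by 5 where Section 4.3.2.3 divides by 10.

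The ratio is one of five immunogenicity parameters reported per age group. The gap between the readings grows with the share of subjects who start undetectable, so it could also alter the comparison across age groups. Section 5.4 allows two steps: "A first analysis of the immunogenicity and safety data from the 100 adult subjects will be performed once data are available", with all subjects analysed later. In principle the two steps could use different rules, or the rule could be settled after adult titres are known.

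**Working it through.** **Inputs.** LLOQ = 10 (Section 4.1.2). A value below LLOQ counts as 5 (Section 4.3.2.1). The fold-rise branches come from Section 4.3.2.3, and 95 evaluable subjects per age group from Section 5.5. The SAP states no titre ratio, so there is no figure of its own to reproduce.

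**The two readings.** Plain ratio: post value / baseline value, both from Section 4.3.2.1. Fold-rise: the four branches of Section 4.3.2.3.

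| Baseline to post | Plain ratio | Fold-rise |
|---|---|---|
| <10 to 10 | 10/5 = 2 | 10/10 = 1 |
| <10 to 40 | 40/5 = 8 | 40/10 = 4 |
| <10 to 80 | 80/5 = 16 | 80/10 = 8 |
| 10 to 40 | 40/10 = 4 | 40/10 = 4 |
| 20 to <10 | 5/20 = 0.25 | 5/20 = 0.25 |
| <10 to <10 | 5/5 = 1 | 1 |

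With concordant duplicates the readings differ only for an upward crossing, and there always by a factor of 2.

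**Group effect.** Let q be the share of subjects with baseline <10 and post ≥10. The geometric mean averages logs, so plain GM ratio / fold-rise GM ratio = 2^q. The SAP gives no q; over an assumed range:

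| q | 0.1 | 0.25 | 0.5 | 0.75 | 1.0 |
|---|---|---|---|---|---|
| 2^q | 1.07 | 1.19 | 1.41 | 1.68 | 2 |

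**Discordant duplicates.** The assay section says of the duplicates that "the two values, which cannot differ by more than a two-fold dilution, are reported". A bleed read as <10 and 10 has geometric mean √(5 × 10) = 7.07, which is still below LLOQ. From 7.07 to 40 the readings are 40/7.07 = 5.66 and 40/10 = 4; from 20 to 7.07 they are 0.35 and 0.25. So 2^q is then only approximate.

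**Seroconversion.** A baseline below 10 is judged by post ≥40, without any ratio. A baseline of 10 or more can reach 4-fold only if the post value is also above LLOQ, where the readings agree. Enumeration confirms this. There are 12 single readings (<10, then 10 doubling to 10240) and 11 means of adjacent pairs, so 23 possible bleed values and 23 × 23 = 529 pairs. The ratio differs in 65 pairs (42 of 42 upward crossings, 21 of 42 downward crossings, 2 of 4 with both values below LLOQ, 0 of 441 with both at or above it). Seroconversion status differs in none.

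**Against precision.** Half-width of the 95% CI on the log10 scale = t(0.975, 94) × SD/√95. For assumed SDs of the log10 ratio of 0.4, 0.5 and 0.6 this is 0.081, 0.102 and 0.122. The gap between readings is q × log10(2) = 0.301q, so it exceeds the half-width once q passes 0.081/0.301 = 0.27, 0.102/0.301 = 0.34 or 0.122/0.301 = 0.41.

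**Which rule does the text support?** Section 4.1.1 names the ratio but does not define it. Section 4.3.2.1 yields one value per bleed and defines no ratio. Section 4.3.2.3 starts from that value and is the only written rule that combines baseline with post. The lists also match by content: mean titre with 4.3.2.1, the ≥40 rate with 4.3.2.2, ratio with 4.3.2.3, seroconversion with 4.3.2.4.

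**The case for a change.** The best case for a change is that the link is never made and that the gap can be larger than the sampling error. The fold-rise rule is cited only for seroconversion, and a literal reader of Section 4.1.1 could defend the plain ratio. Under the fold-rise rule the reported ratio will also not equal the quotient of the reported mean titres, because an undetectable baseline counts as 5 in one and 10 in the other. A reader might take that for an error. One sentence would prevent it.

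What stands is the missing cross-reference, the factor of 2 for a crossing subject, and the mismatch with the quotient of the means. What does not stand is that the SAP holds two rival rules of equal weight. The plain ratio has to be assembled from two sections, neither of which writes it as a formula. If the fold-rise rule served seroconversion alone, its branches for values below LLOQ would do nothing, although the section calls fold-rise a derived endpoint and states a conservative intent. A reading that gives those branches work is the better one. The difference in name is weak evidence, since the ≥40 item is called seroconversion status in Section 4.1.1 and seroprotection in Sections 4.3.2.2 and 5.1.1.2.

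The risk of switching between the adult and the final analysis is conjecture. Both steps fall under one SAP and one biostatistics group, the two-step analysis is only a possibility, and no test or success threshold gives a reason to prefer either value.

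**Conclusion.** No change to the plan is needed. This is a missing cross-reference of the kind that analysts fill sensibly: the only between-bleed formula is in Section 4.3.2.3, and it is deliberately conservative. If an analyst used the plain ratio instead, the result would still be a sound description, because 5 and 10 are both accepted stand-ins for a titre known only to be below 10.

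The effect is confined to one descriptive parameter and its confidence interval. It is at most a factor of 2, and 2^q with concordant duplicates, where q is unknown from the SAP. It can exceed the half-width of the interval if q is above roughly 0.27 to 0.41, under assumed SDs of 0.4 to 0.6. The mean titres before and after vaccination are reported beside the ratio, so the plain quotient remains visible, at least approximately, whichever rule is used. The other four parameters do not depend on the choice, and Section 5.1.1.1 sets no hypothesis that it could affect.

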### 5.1.2 Hypotheses and Statistical Methods for Safety Objective

#### 5.1.2.1 Hypotheses

No statistical hypotheses will be tested.

#### 5.1.2.2 Statistical Methods

The analysis of safety will address the number and percentage of subjects experiencing injection site or systemic ARs or events until 28 days after each injection (solicited reactions from 0 to 7 days and unsolicited AEs/reactions from 0 to 28 days).

The number and percentage of subjects experiencing the following items will be described:

---

a D56 for subjects aged 6 months to 8 years and D28 for subjects aged 9 years or older

**450 – Quadrivalent Influenza Vaccine**

---

- solicited reactions (from 0 to 7 days) after each injection according to intensity, time of onset, and number of days of occurrence
- immediate and delayed unsolicited non-serious AEs (MedDRA System Organ Class and Preferred Term) (from 0 to 28 days) after each injection according to relationship, intensity,
- SAEs, including AESIs, (MedDRA Preferred Term) after each/any injection and throughout the study, related or not, according to seriousness and outcome.

Safety analyses will be performed according to the following age sub-groups following the schedule and the reactogenicity scales applied:

- 6 to 23 months
- 24 to 35 months
- 3 to 8 years
- 9 to 17 years: additionally a subgroup analysis will be done on 9 to 11 years, and 12 to 17 years
- 18 to 64 years
- 65 years or older

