#### 4.3.1 Safety

##### 4.3.1.1 Solicited Reactions

###### 4.3.1.1.1 Daily Intensity

All daily records for solicited reactions will be derived into daily intensity according to the following classification: None, Grade 1, Grade 2, Grade 3, or Missing.

For measurable injection site reactions for subjects aged 6 months to 11 years:

Grade 1:  $> 0$  to  $< 25$  mm

Grade 2:  $\geq 25$  to  $< 50$  mm

Grade 3:  $\geq 50$  mm

For measurable injection site reactions for subjects aged 12 years or older:

Grade 1:  $\geq 25$  to  $\leq 50$  mm

Grade 2:  $\geq 51$  to  $\leq 100$  mm

Grade 3:  $> 100$  mm

For Fever for subjects aged 6 to 23 months:

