**450 – Quadrivalent Influenza Vaccine**

---

Grade 1:  $\geq 38.0^{\circ}\text{C}$  to  $\leq 38.5^{\circ}\text{C}$

Grade 2:  $> 38.5^{\circ}\text{C}$  to  $\leq 39.5^{\circ}\text{C}$

Grade 3:  $> 39.5^{\circ}\text{C}$

For Fever for subjects aged 2 years or older:

Grade 1:  $\geq 38.0^{\circ}\text{C}$  to  $\leq 38.4^{\circ}\text{C}$

Grade 2:  $\geq 38.5^{\circ}\text{C}$  to  $\leq 38.9^{\circ}\text{C}$

Grade 3:  $\geq 39.0^{\circ}\text{C}$

For the derivation of daily intensities the following sequential steps will be applied:

1. Solicited reactions (except Fever) with an investigator presence recorded as “No” and with all daily records missing then all daily intensities will be derived as None.
2. For non-measurable solicited reactions, daily intensities will correspond to daily records reported in the clinical database. For measurable solicited reactions the daily measurements reported in the clinical database will be converted based upon the intensity scales defined above as in the Section 9.2.3.2 of the protocol; this assumes a reaction that is too large to measure (NM, not measurable) is Grade 3. Note: The intensity could be considered “None” (not a reaction) in the analysis despite being considered a reaction by the investigator (e.g., swelling measurement  $> 0$  mm but  $< 25$  mm for subjects aged  $\geq 12$  years).

Missing measurements (for temperature or length) will not be replaced.

The maximum intensity during the solicited period will be computed without considering the ongoing period. If the solicited period is D0 through D7, for an ongoing event at D7, the intensities after D7 will not be considered.

Note: The maximum intensity on the ongoing period is derived from the record of the maximum intensity/measurement after the end of the solicited period following the rule described above.

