**4.3.1.1.3 Presence**

Presence is derived from the maximum overall intensity on the period considered:

- None: No presence
- Grade 1, Grade 2, or Grade 3: Presence
- Missing: Missing presence

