**4.3.1.1.4 Time of Onset**

Time of onset is derived from the daily intensities computed as described in Section 4.3.1.1.1. It corresponds to the first day with intensity of Grade 1, Grade 2, or Grade 3.

Note: If a reaction is not continuous (i.e., reaction occurs over two separate periods of time intervened by at least one daily intensity Missing or None) then the time of onset is the first day of the first occurrence.

Time of onset will be categorized and presented as periods of D0 to D3 and D4 to D7.

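### Does the pooled 9 to 17 years safety row need changing because the redness and swelling scale changes at 12 years?

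*SAP*

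**What the plan says.** Section 5.1.2.2 introduces the safety age groups thus: "Safety analyses will be performed according to the following age sub-groups following the schedule and the reactogenicity scales applied". Six groups follow: 6 to 23 months, 24 to 35 months, 3 to 8 years, 9 to 17 years, 18 to 64 years, and 65 years or older. The 9 to 17 years entry carries the extra split: "9 to 17 years: additionally a subgroup analysis will be done on 9 to 11 years, and 12 to 17 years".

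Section 4.3.1.1.1 gives two size scales for redness and swelling. One is headed "For measurable injection site reactions for subjects aged 6 months to 11 years", the other "For measurable injection site reactions for subjects aged 12 years or older". They agree with Tables 4.2 and 4.3. A note in the same section says that a measurement above 0 but below 25 mm at 12 years or older may be treated as None in the analysis. Section 4.3.1.1.7 repeats the point for ongoing reactions.

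Later variables are built on these grades. Section 4.3.1.1.3 states "Presence is derived from the maximum overall intensity on the period considered". Section 4.3.1.1.4 says of time of onset "It corresponds to the first day with intensity of Grade 1, Grade 2, or Grade 3". Section 4.3.1.1.5 counts days of occurrence in the same way.

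**The concern.** The lead-in says that the groups respect the reactogenicity scales. Five of the six do: each falls under a single set of scales, and the cut at 24 months sits exactly where the infant scales end. Only 9 to 17 years straddles a change, and there the scale-consistent bands appear as an additional analysis.

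For redness and swelling, the pooled 9 to 17 years row is then a rate on neither scale. Presence, onset, duration and grade would all combine two definitions, and the row would vary with the proportion aged 9 to 11, which the SAP does not fix, even if reactions were identical at every age. The safety objective in section 2.2 is descriptive by age group, so a reader could take this row for a rate with one meaning. Injection site totals containing redness or swelling would inherit the mixture. No such total is listed as a row; it is inferred from the opening of section 5.1.2.2, which counts the "number and percentage of subjects experiencing injection site or systemic ARs or events until 28 days after each injection".

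**Working it through.** **1. The plan's own figures.** The SAP's only safety precision statement (section 5.5) is a 0.95 probability of detecting an event of 3% frequency in 100 subjects. It reproduces: 1 − 0.97^100 = 0.952. It is not in dispute and does not bear on the scale question.

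**2. The two scales applied to the same measurement** (section 4.3.1.1.1):

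| Largest measurement | Age 11 | Age 12 |
|---|---|---|
| 10 or 24 mm | Grade 1 | None |
| 25 or 40 mm | Grade 2 | Grade 1 |
| 50 mm | Grade 3 | Grade 1 |
| 60 or 100 mm | Grade 3 | Grade 2 |
| 101 mm | Grade 3 | Grade 3 |

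They agree only at 0 mm and above 100 mm.

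**3. What is affected.**
- Redness and swelling: presence, grade, onset, days of occurrence and ongoing status.
- Measurable unsolicited non-serious events whose preferred term is on the solicited list. Section 4.3.1.2.2 grades them on the same scales, and section 4.3.1.2.1 removes Grade 0 events from the analysis.
- Pain by grade, but only through the wording of the grades (Tables 4.2 and 4.3). Occurrence of pain has no size cut-off.
- Not fever or the other solicited systemic reactions, which use one scale from 2 years (Table 4.5).

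**4. Size of the mixing.** Let p25 be the proportion whose largest reaction is at least 25 mm, d the proportion whose largest reaction is above 0 but below 25 mm (both taken as equal at all ages), and w the share aged 9 to 11.

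Pooled rate = w(p25 + d) + (1 − w)p25 = p25 + d·w.

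The SAP gives neither d nor w, so both are assumed:
- w from 25% to 50%: shift = 0.25d, that is 1.25, 2.5 or 5.0 points for d = 5%, 10% or 20%.
- w = 1/3 (equal numbers per year of age, 3 of 9 years) and d = 10%: the pooled rate is 3.3 points above the rate at 25 mm or more, and 6.7 points below the rate above 0 mm.
- A more extreme case: 20% with any reaction above 0 mm, one tenth of them reaching 25 mm. The rates are then 20% at 9 to 11 and 2% at 12 to 17 years. The pooled rate is 5.6%, 8.0%, 11.0% or 16.4% for w = 20%, 33%, 50% or 80%.

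For scale, the exact 95% interval for 12/100 is 6.4% to 20.0%, a width of 13.7 points. The shifts in the first bullet are smaller than its distance from 12% to either limit (5.6 and 8.0 points). The range in the last bullet (16.4 − 5.6 = 10.8 points) is larger than either distance.

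**5. What the planned outputs already show.** Section 5.1.2.2 reports solicited reactions by intensity, and the split at 12 years belongs to the same list of safety analyses. Reactions of 25 mm or more are Grade 2 or 3 at 9 to 11 years and Grade 1, 2 or 3 at 12 to 17 years. A reader who wants one definition for the whole cohort can add those two counts and divide by the total number with data. In the last bullet of step 4, the 20% and the 2% would both be printed, whatever the age mix.

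**6. What promoting the subgroups would cost.** If 33 of 100 are aged 9 to 11 (assumed), exact 95% interval widths near 50% are 35.7 points (16/33) and 24.9 points (33/67), against 20.3 points (50/100).

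**The case for a change.** The strongest case for a change runs as follows. The plan states a grouping rule, applies it at 24 months and does not apply it fully at 12 years. The shift is one of definition, not chance, so the confidence interval around the pooled rate does not cover it. Planned subgroups do not tell a reader what the pooled row means. The remedy would be one sentence and one footnote, with no new data.

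The arithmetic and the point about the interval stand. The rest is weaker.

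- The lead-in names two bases for grouping, schedule and scales. The 9 to 17 years group is an enrolment cohort on one schedule (section 3.1), and its split at 12 years follows the scales. Read whole, the entry does what the lead-in promises. Nowhere is the pooled row called the main one.
- The pooled row does have a meaning: subjects with a reaction on the scale for their age. Section 4.3.1.1.1 fixes that rule and warns about measurements below 25 mm.
- It is true that the pooled row cannot be set beside the 3 to 8 years or the adult row for these reactions. But those two rows cannot be compared with each other either, since one uses Table 4.2 and the other Table 4.3. That comes from having age-specific scales, not from pooling.
- The remedy would only re-rank outputs already planned. A footnote of this kind belongs in the table shells.

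**Conclusion.** The observation is correct: pooled 9 to 17 years figures for redness and swelling count reactions on two scales. By inference, so does any injection site total containing them, and so do measurable unsolicited events graded on the same scales. No change to the plan is needed. Results on a single scale, split at the right age, are already planned in the same line; grading is explicit for every subject; no hypothesis is tested (section 5.1.2.1); and the early safety reviews use line listings (section 5.4), not pooled percentages.

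The size is unknown from the SAP. Under the assumed inputs it runs from 1.25 to 5.0 points when the share aged 9 to 11 moves from 25% to 50%, and to about 11 points in the extreme case. All of this assumes the same distribution of reaction sizes at all ages. No planned result or conclusion is shown to change. For these items, read the 9 to 11 and 12 to 17 years results first, and take any pooled figure as graded on each subject's own age-specific scale.
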